Center for Diabetes Technology

Feasibility of a Decision Support System To Reduce Glucose Variability In Subjects with T1DM

NCT02558491
Version Date: 10-14-2016

A. Purpose/Objectives

The purpose of this study is to demonstrate the safety and feasibility of a decision support system aimed at reducing glucose variability in T1DM patients using continuous subcutaneous insulin infusion (CSII) or multiple daily injections (MDI). The system will be deployed on our portable medical application platform (DiAs) and will include the following elements:

1. An insulin pump or MDI treatment parameters optimization routine, using a month of collected CGM/insulin/meal data
2. An exercise risk warning system, capable of predicting hypoglycemia at the onset of physical activity and advising on mitigating treatments such as insulin adjustment or carbohydrate consumption
3. A smart bolus calculator based on CGM glucose measurements and insulin sensitivity estimation.

Primary Specific Aim:

To demonstrate feasibility and safety of a glucose variability-reducing decision support system, measured by non-inferiority of use of the system compared to standard SMBG-informed CSII or MDI therapy in terms of occurrence of hypoglycemia and percent time spent between 70 and 180 mg/dl as measured by blinded CGM.

Secondary Specific Aims:

To assess the effect size of using the GV advisory system compared to standard CSII or MDI therapy in terms of:

- Occurrence of hypoglycemia during and immediately after exercise
- Glycemic excursion post meals

B. Study Design Overview

Subjects: The study is intended to complete up to 20 subjects with Type 1 Diabetes Mellitus who use continuous subcutaneous insulin infusion (CSII) and up to 20 subjects with Type 1 Diabetes Mellitus who use multiple daily injections (MDI). The study will be a randomized cross-over design with a Control and Experimental admission. The order of the admissions will be randomized. It is estimated that there will be a higher than normal rate of screen failures, dropouts, or withdrawals, thus we intend to set a recruiting target of **70 subjects**.

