Subjects will use their own insulin parameters, including basal rate or basal insulin dose insulin sensitivity factor and carbohydrate ratio, and determine their own insulin usage during the Control admission.

MDI subjects will be provided with an insulin pen (NovoPen Junior, NovoPen Echo, or Companion Medical inPen Smart Pen) with short-acting insulin for treatment during the Experimental admission. These pens are capable of delivering insulin in 0.5 unit increments and are FDA approved but for the Smart Pen which is under 510(k) review (see letter of Authorization). If this option is selected, the Companion Medical pen, known as the InPen, will be used in the trial. This insulin pen contains computer chip technology built into the base and

has Bluetooth LE wireless capability. It will collect the subject's data and then transmits it to an app that contains a dose calculator and also calculates real-time insulin on board (IOB). The insulin pen has remote monitoring, permitting the subject to inform the study team of their insulin dose, BG and carbohydrates. An inPen User Guide will be available to all MDI subjects if this smart pen is used in the trial. If this pen is not available at the time of the trial, a pen that can deliver in 0.5 unit increments will be used, such as the Lilly Luxura insulin pen.

The study is also designed to test the capacity of our exercise advisory system to avoid or limit exercise-induced hypoglycemia, by challenging the subject with two 3x15min exercise bouts.

Study Diagram

Visit 1: Screening Visit. All subjects will be consented and receive a history and physical. Study eligibility will be reviewed. After a subject completes the screening criteria, the subject will be randomized to the Experimental or Control admission first.

Visit 2: CGM Placement & Training. All subjects will receive training on the use of the continuous glucose monitor (CGM) and study glucometer prior to the Experimental admission. Approximately 28 days of **blinded** CGM data will be collected with a total of 14 valid days needed to participate in the research house/hotel admission. Visit 1 and 2 can be done on the same day.

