As a safety/feasibility investigation, this study is not powered to a specific outcome. Nonetheless, based on prior work and computer simulations we estimate the likely effect size to be large (around 0.7); we therefore have chosen a sample size of 15-20 subjects for each group (CSII and MDI). Using a power analysis with a fixed sample size, significance and 0.8 power, this would allow us to detect an effect size larger than 0.67. In prior studies, 15 subjects have also been considered by regulatory bodies as an appropriate sample size to demonstrate safety in transitional settings for CGM based insulin dosing.

Investigational Site

The University of Virginia has granted the Center for Diabetes Technology the use of a facility designated Research House to perform outpatient studies related to the Artificial Pancreas Project. The facility is located 2.2 miles from the University of Virginia Emergency Department. It is a 4 bedroom/4 bath home with sleeping quarters on the first and second floors. The study team may test up to 3-5 study participants at the same time in the research house.

Minimal Staffing Requirements

At all times, a minimum of one registered nurse, trained in the execution of the protocol as well as in the management of hypo- and hyperglycemia, and a technician, trained in the use and maintenance of the DiAs system will be present during the entire trial. In addition, one of the study physicians and one senior engineer will be on call during the entire admission, with backup MDs and engineers available if the primary contact is unable to be reached. During exercise, there will be a minimum of one nurse per two subjects and one technician per two subjects on site. In the event of five study subjects tested during a single admission, two medically trained personnel will be available during the trial.

D. Study Duration

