5. The study team will confirm that the subject brought his/her insulin, insulin pump or MDI supplies, and regular medications. The study team will also confirm the absence of a febrile illness and absence of acetaminophen use while wearing the CGM sensor. The subject may be rescheduled if these criteria are not met.
6. Female subjects of childbearing potential will perform a urine pregnancy test. If positive, the subject will discontinue study participation. The subject will be asked to seek confirmation of the test and the appropriate medical care.

Admission Procedures

Day 1

1. **General Information:** During both admissions, the subject will wear a blinded Dexcom CGM connected to DiAs for remote monitoring capabilities. The staff will remotely monitor the subject using the remote monitoring website. DiAs will be programmed with the home insulin dosing parameters during the Control admission and with the optimized insulin dosing parameters during the Experimental condition. DiAs will be used for meal insulin dosing advice for both admissions and for pre-exercise advice during the Experimental admission. DiAs will be informed of any BG values, meals, carb treatments, correction doses, or snacks during the admission. The DiAs system will be initiated prior to dinner.
 - a. **Experimental Admission** – The DiAs will be programmed with the new optimized basal rates or basal insulin dose (entered as a basal rate U/hr = Lantus, Tresiba, Levemir dose/24hr), insulin sensitivity factor(s), and carbohydrate ratio(s). These new parameters will be used for insulin dosing advice during the entire admission. MDI users will use the study insulin pen for meal insulin dosing and the home insulin pen or syringe for Lantus (glargine), Tresiba [degludec], or Levemir [Detemir] dosing. Pump users will use the home pump for both meal insulin dosing and basal insulin administration during the admission.
 - b. **Control Admission** – The study subject will use the home basal/bolus MDI or CSII insulin regimen via the home insulin pens or pump and determine the amount of insulin to give for the entire admission per the subject's home carb counting parameters and as calculated by the DiAs meal screen.

2. **Dinner:** A dinner meal will be provided between 18:00-19:00. The subject will define the amount of carbohydrates at the dinner meal. The amount of carbs designated by the subject will be consistent between the Control and Experimental admission.

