2. Meals will be replicated during each admission.
3. The subject or study staff will enter the amount of carbohydrates into the DiAs meal screen for each meal. Carbohydrate amounts may be underestimated prior to exercise if that is the usual home routine.
4. Snacks will only be permitted if advised by DiAs prior to exercise and per the usual routine prior to bedtime. Snacking between meals will not be permitted.

Meal	Carb	Fat	Protein	Carb (g/kg)	Fat (g/kg)	Protein (g/kg)
Day 1						
Dinner	High	Low	Moderate	1	0.2	0.27
Day 2						
Breakfast	Low	Low	Moderate	0.5	0.14	0.27
Lunch	Moderate	High	Moderate	0.75	0.46	0.27
Dinner	High	High	Moderate	1	0.53	0.27
Day 3						
Breakfast	Low	Low	Moderate	0.5	0.14	0.27
Lunch	Moderate	Low	Moderate	0.75	0.17	0.27

Figure 2: Meal Composition

Equipment Specifications

1. All study equipment including the DiAs cell phone, computers, insulin pump (for CSII subjects), and CGM receivers will be set to the same time using an atomic clock as a reference.
2. The study team will train the subject on the DiAs interface until all questions are answered. However, study staff will supervise all interactions with the DiAs, including entering information for meal dosing, FSBG results, hypoglycemia treatments and temporary basal

rates.

3. The CGM tracing will be blinded on the DiAs and on the CGM receiver.
4. Subjects will wear a heart rate monitor during each exercise session.

Blood Glucose Measurements

- The subject will be instructed that all fingersticks should be preceded by hand washing with warm water and a dry towel. The subject will be instructed to obtain fingerstick, avoiding alternative sites, when obtaining blood values. The first drop of blood will be discarded. The second hanging drop will be used to measure the glucose level.
- The subject will be reminded that all treatment decisions should be based on fingerstick values and not on CGM values.
- Once a fingerstick is obtained for any reason during the admissions, the Glycemic Treatment Guidelines (Appendix A-6) will be followed to determine timing of subsequent fingersticks.
- Scheduled times: prior to meals and snacks, before and after each 15 minute exercise bout, and at bedtime (23:00).
- Prior to calibration of CGM and/or if calibration is requested by CGM.
- The subject may request any additional fingersticks as desired.

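### For MDI subjects who usually snack before exercise, Control is not standard therapy: a pre-exercise snack needs DiAs advice, and Control gives none

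*Combined protocol and SAP*

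**What the plan says.** Meals item 4 sets the snack rule for both admissions: "Snacks will only be permitted if advised by DiAs prior to exercise and per the usual routine prior to bedtime". It then bars snacks between meals. Exercise starts at about 11:00 on Day 2 and 10:00 on Day 3, between breakfast and lunch.

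General Information (Admission Procedures, Day 1) splits the role of DiAs: "DiAs will be used for meal insulin dosing advice for both admissions and for pre-exercise advice during the Experimental admission". The Day 2 and Day 3 Exercise Session items accordingly list DiAs snack advice under the Experimental admission only.

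The Control text on breakfast (Days 2 and 3) lets a subject set a temporary basal rate before exercise as they usually would. Meals item 3 and the breakfast items let any subject, in either admission, announce less breakfast carbohydrate than is eaten. No Control text provides for a usual pre-exercise snack.

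Section A counts carbohydrate among the tools of the exercise component, described as "advising on mitigating treatments such as insulin adjustment or carbohydrate consumption". The secondary aim there is "To assess the effect size of using the GV advisory system compared to standard CSII or MDI therapy in terms of" two outcomes, the first being "Occurrence of hypoglycemia during and immediately after exercise".

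**The concern.** The protocol keeps the usual home routine for temporary basal rates, breakfast carbohydrate announcement and the bedtime snack. The usual pre-exercise snack is the exception. This matters mainly for MDI subjects, who have no basal rate to reduce and for whom carbohydrate is the only exercise measure that DiAs offers.

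Take an MDI subject who normally eats something before exercise. In Control the snack is withheld; in the Experimental admission DiAs can give one. The contrast then mixes two things: the value of the advice, and simply being allowed to eat beforehand. The aim is to estimate an effect size against standard therapy, so the meaning of the estimate depends on the comparator. A Control with less protection than the subject's own routine would tend to show more exercise hypoglycemia and so flatter the system.

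**Working it through.** **1. Measures open before exercise, side by side** (General Information; Day 2 and Day 3 Breakfast and Exercise Session; Meals items 3 and 4; Blood Glucose Measurements)

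| Measure | Control, MDI | Control, CSII | Experimental |
|---|---|---|---|
| Under-announce breakfast carbohydrate | yes | yes | yes |
| Usual temporary basal rate | not applicable | yes | not listed; DiAs may advise 0% for 1 hour (CSII) |
| Usual preventive snack | no | no | no |
| DiAs-advised snack | no | no | MDI: 12-16 g at mild-moderate risk, 24-32 g at high risk; CSII: 12-16 g at high risk |
| Hypoglycemia treatment when due or requested | yes | yes | yes |

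The snack rule names no admission. A habitual snacker in the Experimental admission also goes without when DiAs detects no risk, but there the decision is the system's advice, which is what is being tested. In Control nothing replaces the habit.

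**2. When the rule has an effect in Control**

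Both days require a glucose of at least 80 mg/dL to start a bout.

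- Day 2: a value below 100 mg/dL is treated immediately before and during exercise. The snack rule therefore matters only at 100 mg/dL or above with no treatment requested.
- Day 3: the exercise item applies the 100 mg/dL limit only after exercise has started. Blood Glucose Measurements also applies the treatment guidelines when CGM is below 80 and the fingerstick is below 100 mg/dL. A start at 80-99 mg/dL may therefore already be due for treatment. If it is not, and the value stays below 100, it is treated at the next fingerstick, one 15-minute bout later.
- Both days: a subject may ask for hypoglycemia treatment at any time.

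**3. How many sessions could be touched**

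Inputs: 15-20 MDI subjects (section C) and two exercise sessions per admission.

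- MDI Control sessions: 15 × 2 = 30 to 20 × 2 = 40.
- Let f be the share of MDI subjects who usually snack, which the documents do not give. With 20 subjects, assumed values of f = 0, 25%, 50% and 100% give 0, 5, 10 and 20 subjects, or 0, 10, 20 and 40 sessions. These are upper bounds, before removing sessions where treatment is due or requested.
- If withholding the snack changes each such subject's Control outcome by d on average, the MDI Control mean moves by f × d. Neither f nor d is in the documents, so the product cannot be computed and zero is possible.

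**4. The plan's only effect-size figure**

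Of its sample size and 0.8 power, section C says "this would allow us to detect an effect size larger than 0.67". A paired t-test with n = 20 and an assumed two-sided alpha of 0.05 gives 0.66, so the figure reproduces. It is tied to no outcome, whereas this outcome is an occurrence of hypoglycemia. It is not used here to scale the problem.

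**5. Time from exercise to lunch (12:00-13:00), for the cost of a fix**

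- Day 2: start 11:00, so 60-120 minutes from the start. After 45 minutes of exercise, 15-75 minutes from the end.
- Day 3: start 10:00, so 120-180 minutes from the start and 75-135 minutes from the end.
- Six meals are served per admission, and two of them are lunches after exercise.

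**The case against.** The strongest reply is that the restriction is deliberate. Exercise advice, including carbohydrate, is part of the tested system, so Control should lack it. Control is described in terms of insulin: subjects "determine their own insulin usage during the Control admission". Meals are replicated between admissions and an evening snack, if taken, must be too. Barring ad hoc daytime snacks fits that scheme. This stands as a reason for the rule, but it does not make the result a comparison with standard MDI therapy. If the rule stays, the description of the comparator has to change.

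A second reply is that MDI subjects in Control are not unprotected. They can under-announce breakfast carbohydrate, which lowers the meal dose before exercise, and can request treatment. This also stands and reduces any effect. It does not remove it: the designated breakfast carbohydrate must be consistent between admissions, and treatment on request is not a routine snack at 100 mg/dL or above. How freely requests are met may depend on Appendix A-6, which was not available.

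Third, exercise hypoglycemia is a secondary aim, is absent from the Endpoints list, and belongs to a study not powered for any specific outcome. That is correct and is why the point is minor.

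**Conclusion.** The point holds as a minor one. Followed as written, the snack rule leaves MDI subjects who usually snack before exercise with a Control that is something less than standard therapy for the secondary exercise comparison. The likely direction favours the system. The size is unknown and may be nil. It rests on two quantities that the documents do not give (the share of habitual snackers and the protection the snack provides) and on Appendix A-6.

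A reader might infer more, and the documents do not support it:

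- **That the primary endpoint is biased.** LBGI is computed from CGM data, but the plan does not state the window, and nothing shows that a missing snack would move it. No LBGI effect is claimed.
- **That the CSII comparison is biased in the same direction.** Pump users who snack also lose the snack, but they keep their usual temporary basal rate, so no direction can be stated.
- **That every Day 3 start at 80 mg/dL or above goes untreated.** The CGM-triggered rule and treatment on request can apply before the first bout.
- **That the distortion can be sized against the 0.67 in section C.** That figure does not belong to this outcome.

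**What to change.** Amend Meals item 4 so that, before exercise, a snack may be taken on DiAs advice in the Experimental admission and according to the subject's home habit in Control, parallel to the temporary basal allowance. Log it in DiAs with time and grams. The entry is already required: "DiAs will be informed of any BG values, meals, carb treatments, correction doses, or snacks during the admission". Because snacks without insulin go on the hypoglycemia treatment screen, add a label that separates preventive snacks from hypoglycemia treatment.

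If the sponsor prefers to keep the restriction for standardisation, state the exercise result as being against a Control without routine pre-exercise snacks, not against standard therapy.

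In either case, tabulate carbohydrate taken before and during exercise by admission, separately for MDI and CSII. A question on the usual pre-exercise routine, added to the diabetic history at screening, would also supply the missing share of habitual snackers.

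The cost is a sentence, a log label and a table, plus the optional question. Allowing the snack makes Control somewhat more variable. The snack may also carry over into the postprandial glucose area after lunch on Days 2 and 3 (two of six meals), as a DiAs-advised snack already can in the Experimental admission; showing post-lunch results separately from the other four meals would expose this. Restating the comparator has neither drawback.

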- Study personnel may also request additional fingersticks at their discretion.
- BG treatments will be based on Glycemic Treatment Guidelines (Appendix A-6) although hypoglycemic treatments can occur at any time per the subject's request.
- If CGM <80 mg/dL, SMBG will be performed every 15 minutes. If SMBG <100 mg/dL, the Glycemic Treatment Guidelines (Appendix A-6) will be applied.
- If CGM >300 mg/dL, SMBG will be performed every 60 minutes. If SMBG >300 mg/dL, the Glycemic Treatment Guidelines (Appendix A-6) will be applied.
- In case of remote monitoring unavailability or in case of CGM failure (an alert will sound on the DiAs and on the remote monitoring), SMBG will be collected at bedtime, 3am and 7am until the issue is resolved.
- Calibrations of the CGM will be per manufacturer guidelines. Hypoglycemia treatment (e.g. glucose tablets, glucose gel/liquid, and a glucagon emergency kit) will be available for

treatment at all times.

- The subject will have access to ad lib glucose-free beverages.
- A study MD will be available for any clinical concerns.
- The Senior DiAs Engineer with remote monitoring capability will be available if needed to view the study from another location. A DiAs trained technician will be on site for any system issues.
- The subject will be accompanied by a medically qualified staff member and a technician during the admissions.

SAFETY MONITORING / RISK ANALYSIS

- **Monitoring Procedures by Staff**

1. CGM values are updated onto DiAs every 5 minutes.
2. Study staff will be constantly monitoring the CGM and subject-entered SMBG values from the remote monitoring website and alert nursing and physician staff when the CGM is <80 or >300 mg/dL.
3. If CGM < 80 mg/dL, SMBG will be performed every 15 minutes. If SMBG >80 mg/dL, the Glycemic Treatment Guidelines (Appendix A-6) will be applied during both the Experimental and Control admissions.
4. If CGM >300 mg/dL, SMBG will be performed every 60 minutes. If SMBG >300 mg/dL, the Glycemic Treatment Guidelines (Appendix A-6) will be applied Experimental and Control Admissions.
5. The DiAs trained technician will monitor the system for the first floor of the research house/hotel during the entire admission.
6. Medical personnel and emergency supplies are on the first floor of the research house/hotel but the study staff periodically round subjects' rooms on both floors during the overnight hours.

- **Glucose Monitoring Risk:**

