The Outpatient Emergency Plan will go into effect should a catastrophic event occur during the study admissions. A catastrophic event is defined as any event that requires emergency treatment by medical professionals that exceed the expected parameters of the protocol. A copy of this plan will be located at the monitoring desk. Staff will be aware of its location at all times.

In the unlikely event of a disruption in 911 phone service, the sites will contact their local non-emergency number (e.g. Charlottesville-UVA-Albemarle Emergency Communications Center can be reached via their non-emergency number [contact]). This number feeds into their main call area where 911 dispatchers are available 24/7.

Event	RN Response	Tech Response
Respiratory Arrest	1) Tell Tech to call 911 2) Begin Basic Life Support	Refer to Study Physician
Cardiac Arrest	1) Tell Tech to call 911 2) Begin Basic Life Support	Refer to Study Physician
Severe Hypoglycemic Event as defined by hypoglycemia accompanied by unconsciousness or seizure	1) Tell Tech to call 911 2) Administer glucagon IM (described in Glycemic Treatment Guidelines Appendix A-6) 3) Remove study pump	Refer to Study Physician
Severe Hyperglycemic Event as defined by β -ketone level ≥ 3.0 mmol/L	1) Discuss correction dose of insulin to administer s.c. via syringe with study M.D. 2) Encourage P.O. water intake 3) Remove study pump and start home insulin pump 4) Go to nearest medical facility for evaluation and treatment.	Refer to Study Physician

Table 3: Outpatient Emergency Plan

ENDPOINTS

We assess the risk to the subject by computing the two classical hypo and hyperglycemia risk indices LBGI and HBGI, based of the blinded CGM data, retrofitted to the SMBG point (see DelFavero et al. JDST 2015). Gaps of less than 3h will be filled using spline based interpolation. LBGI is the primary endpoint.

LBGI and HBGI are measures of glycemic risk that were developed by our groups in the late 1990s and have been shown to be predictive of increased frequency of severe hypoglycemia and increased HbA1c. Detailed formula can be found in Kovatchev et al. Diabetes Care 1998.

In addition we will capture:

- Quality of glycemic control using the percent time spent between 70mg/dl and 180mg/dl.
- Meal insulin coverage will be assessed using Area Under the glucose Curve in the postprandial state.

CLINICAL PROTOCOL

- Glucose variability will be assessed using the Risk Index (sum of LBGI and HBGI).

SUCCESS CRITERIA / GOAL

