As a general rule, a session will be considered useful for data analysis if the subject completes more than 80% of the active study protocol. Subjects completing less than 80% of the protocol may be rescheduled.

Safety and feasibility will mean that using our system, subjects will not increase either their risk of hypoglycemia as measured by LBGI (non-inferiority claim)

STATISTICAL ANALYSIS PLAN

All variables are continuous and though bounded by 0 unlikely to be close to their lower bound, therefore we will compare the control and experimental admissions using a paired Student t-test for equality of mean. Nonetheless, LBGI may be very low in some subjects during the control admission. If such effect is observed in more than 5 subjects, LBGI will be studied using the Wilcoxon signed rank test.

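### Staff rescue can move harm from LBGI into rescue carbohydrate, and the plan compares only LBGI; a paired comparison of rescue use should stand beside it

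*Combined protocol and SAP*

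**What the plan says.** - **Endpoint and success.** Under Endpoints, "LBGI is the primary endpoint", computed from blinded CGM retrofitted to fingersticks. The other listed measures are HBGI, time in 70 to 180 mg/dL, postprandial area under the curve and the Risk Index. Under Success Criteria, "Safety and feasibility will mean that using our system", "subjects will not increase either their risk of hypoglycemia as measured by LBGI (non-inferiority claim"). No margin is given.
- **Test.** The SAP will "compare the control and experimental admissions using a paired Student t-test for equality of mean", or use the Wilcoxon signed rank test if LBGI is very low in more than 5 subjects.
- **Rescue.** Under Blood Glucose Measurements, CGM below 80 mg/dL starts fingersticks every 15 minutes, and then "If SMBG <100 mg/dL, the Glycemic Treatment Guidelines (Appendix A-6) will be applied". Under Monitoring Procedures by Staff, the condition after the same CGM trigger is a fingerstick above 80 mg/dL. The guidelines apply at Visits 4 and 5. In the Exercise Session items, fingersticks below 100 mg/dL are treated. Subjects may also ask for treatment at any time.
- **Recording.** Under Admission Procedures, Day 1, "DiAs will be informed of any BG values, meals, carb treatments, correction doses, or snacks during the admission". The adverse event definition covers only hypoglycemia needing another person's help because of altered consciousness, and a later section restricts recording to events both related and serious.

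**The concern.** Rescue is triggered by the low glucose that LBGI measures. An admission that produces more lows will draw more rescue, and each rescue shortens or blunts the low that would have raised LBGI. If the optimised parameters are harmful, part of the harm therefore moves out of the primary endpoint and into treatment use. Ordinary rescues are neither an endpoint nor an adverse event, so no planned analysis would show the shift. The trial could report that hypoglycemia risk was not increased when the LBGI result was held down by extra carbohydrate given by staff, support that would not be present in ordinary use of the system.

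**Working it through.** **The plan's own figure.** The sample size section says "Using a power analysis with a fixed sample size, significance and 0.8 power", "this would allow us to detect an effect size larger than 0.67". Alpha is not given; I assume 0.05 two-sided. For a paired t-test with n = 20, the noncentrality is 0.67 × √20 = 2.996 and power is 81.1%; the effect detectable with 80% power is 0.660. The figure is reproduced at n = 20. At n = 15 the detectable effect is 0.778. This is a figure for detecting a difference, not non-inferiority power.

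**Model of attenuation.** Let the unrescued Experimental minus Control difference be D, in units of the unrescued SD of the paired difference, and let rescue leave a fraction f of it. The documents give no value for f, the SD, the margin or the rescue rate, so all are assumed. Two cases bracket the effect on the SD: unchanged, or multiplied by the same f.

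**A. Claim against a fixed margin M.** Set D = M, so non-inferiority should be declared 2.5% of the time (one-sided 0.025). The noncentrality is M(1 − f)√n if the SD is unchanged and M(1 − f)√n / f if it shrinks by f. For n = 20, M = 0.67 and f = 0.5 these are 0.335 × 4.472 = 1.498 and 0.67 × 4.472 = 2.996.

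| f (M = 0.67, n = 20) | SD unchanged | SD shrinks by f |
|---|---|---|
| 1 | 2.5% | 2.5% |
| 0.75 | 10.6% | 15.6% |
| 0.50 | 29.6% | 81.1% |
| 0.25 | 56.9% | about 100% |

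With f = 0.5 and M from 0.3 to 1.0, the range is 9.3% to 56.4% (SD unchanged) or 24.6% to 98.9% (SD shrinks). At n = 15, M = 0.67 and f = 0.5 the figures are 22.7% and 67.5%.

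**B. Equality test as written.** For unrescued harm D = 0.67 and n = 20, the noncentrality is f × 0.67 × √20 if the SD is unchanged. The chance of flagging harm is then 81.1%, 56.9%, 29.6% and 10.6% at f = 1, 0.75, 0.5 and 0.25. If the SD shrinks by f, f cancels and the chance stays at 81.1%. The Wilcoxon statistic is likewise unchanged when every difference is multiplied by the same positive constant.

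**C. Illustration.** Simulated 48-hour traces, with assumed glucose dynamics, low-glucose index and rescue response:

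| Downward shift in Experimental | Raw difference, no rescue → rescue | Standardised difference | Rescues per admission, Control v Experimental |
|---|---|---|---|
| 0 mg/dL | 0.002 → −0.002 | 0.001 → −0.009 | 7.0 v 7.0 |
| 10 mg/dL | 0.845 → 0.064 | 0.295 → 0.308 | 7.0 v 9.2 |
| 20 mg/dL | 1.969 → 0.145 | 0.596 → 0.601 | 7.0 v 12.1 |

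The retained raw fractions are 0.064/0.845 = 7.6% and 0.145/1.969 = 7.4%. The SD fell about as much, so the standardised difference barely moved. The harm reappeared as 2.2 and 5.1 extra rescues per admission. With no true harm, nothing spurious arose. The sizes belong to the assumed model; only the pattern is informative.

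**The case against.** The strongest reply is that rescue is a safety measure applied under common rules, so LBGI with rescue included is a legitimate treatment-policy comparison, in a feasibility study that says it is not powered to a specific outcome. That stands. It is a reason to keep LBGI, but not to read it alone.

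Several stronger readings are tempting and are not supported:

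- **A true 0.67 SD shrinks to 0.47, 0.34 or 0.20 when rescue removes 30%, 50% or 70% of low exposure.** Multiplying 0.67 by 0.7, 0.5 and 0.3 assumes an unchanged SD. If rescue scales both admissions by the same fraction, the SD scales too and the standardised difference stays 0.67.
- **The plan as written makes success too easy.** That is firm only against a fixed LBGI margin, and none is stated. For the written tests it depends on how the SD responds. It also matters only if the system truly increases lows.
- **Every fingerstick below 100 mg/dL is treated before hypoglycemia occurs.** Outside exercise the sequence starts at CGM below 80 mg/dL, the guidelines also set the timing of later fingersticks, and the text of Appendix A-6 is not available here. The second statement of the condition conflicts with the first.
- **The plan judges safety by LBGI alone.** The aims also name occurrence of hypoglycemia, time in range and hypoglycemia around exercise, and there are stopping rules. Only the success sentence rests on LBGI alone.
- **Safety should be claimed only if rescue use is also not increased.** Such a gate needs a decision rule. Counting rescues alone would also favour the Experimental admission, where carbohydrate advised by the system before exercise may replace rescue.

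**Conclusion.** The point holds in a limited form. The documents establish that rescue responds to the signal LBGI measures, that it operates in both admissions, and that no planned analysis counts it although the data are entered in DiAs. If the optimised settings increase lows, the raw LBGI difference will be attenuated and a claim against any fixed margin becomes easier to meet. For the paired t-test or Wilcoxon test as written, sensitivity to harm falls only if the SD shrinks less than the mean difference. The figures above show how the conclusion depends on assumed values of f, M and the SD; they do not estimate this trial's bias. A reader might infer that a system needing twice the rescues would pass; no calculation from the documents shows that. What they do show is that such a difference would appear in no planned analysis. The gap should be closed before safety is claimed, and closing it changes what the safety conclusion can say.

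**What to change.** Leave the rescue rules unchanged. In the SAP:

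1. Pre-specify, as a key supporting safety outcome, the paired Experimental minus Control difference with confidence interval in (a) rescue episodes and (b) total non-meal carbohydrate per admission, from the DiAs log.
2. Show rescue carbohydrate and DiAs-advised carbohydrate both separately and combined, because only in the Experimental admission can advised carbohydrate stand in for rescue.
3. Exclude planned evening snacks. Those taken without insulin are entered through the hypoglycemia treatment screen, so a rule to separate them from rescues is needed.
4. Word the conclusion as hypoglycemia risk by LBGI under staff-supervised rescue, read together with this comparison. Do not state that risk is not increased if rescue or total non-meal carbohydrate is clearly higher in the Experimental admission, and define beforehand what counts as clearly higher.
5. State the LBGI margin if the non-inferiority claim is kept.

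Separately, the two conflicting fingerstick conditions after CGM below 80 mg/dL (below 100 in one place, above 80 in the other) must be reconciled, since the trigger governs how far LBGI is affected.

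The cost is SAP wording, one extra table, some work to separate snacks from rescues, and a slightly harder safety claim. Subjects may request treatment and staff know the admission type, so the rescue count is an open-label measure and should be read as supporting evidence.
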